### **Wound healing complications**

No formal studies of the effect of axitinib on wound healing have been conducted. In Phase 3 study A4061032 with axitinib for the treatment of patients with RCC, all-causality adverse events suggestive of wound healing complications were reported in 4/359 patients (1%).

Treatment with axitinib should be stopped at least 24 hours prior to scheduled surgery. The decision to resume axitinib therapy after surgery should be based on clinical judgment of adequate wound healing.

### **Reversible posterior leukoencephalopathy syndrome/posterior reversible encephalopathy syndrome**

In Phase 3 study A4061032 with axitinib for the treatment of patients with RCC, reversible posterior leukoencephalopathy syndrome (RPLS)/posterior reversible encephalopathy syndrome (PRES) was reported in 1/359 patients (<1%).

RPLS/PRES is a neurological disorder which can present with headache, seizure, lethargy, confusion, blindness and other visual and neurologic disturbances. Mild to severe hypertension may be present. Magnetic resonance imaging is necessary to confirm the diagnosis of RPLS/PRES. In patients with signs/symptoms of RPLS/PRES, temporarily interrupt or permanently discontinue axitinib. The safety of reinitiating axitinib therapy in patients previously experiencing RPLS/PRES is not known.

### **Proteinuria**

In Phase 3 study A4061032 with axitinib for the treatment of patients with RCC, proteinuria was reported in 39/359 patients (11%). Grade 3 or 4 proteinuria was reported in 11/359 patients (3%).

Monitoring for proteinuria will be performed before initiation of, and periodically throughout, treatment with axitinib.

### **Elevation of liver enzymes**

In the first-in-human dose-finding study A4060010, concurrent elevations of alanine aminotransferase [ALT] (12 times the ULN) and bilirubin (2.3 times the ULN), considered to be drug-related hepatotoxicity, were observed in 1 patient who received axitinib at a starting dose of 20 mg twice daily (4 times the recommended starting dose). In Phase 3 study A4061032 with axitinib for the treatment of patients with RCC, no concurrent elevations of ALT (>3 times the ULN) and bilirubin (>2 times the ULN) were observed for axitinib (N=359).

ALT, aspartate aminotransferase (AST) and bilirubin will be monitored before initiation of and periodically throughout treatment with axitinib.

### **Cardiac failure events**

In clinical studies with axitinib for the treatment of patients with renal cell carcinoma, cardiac failure events (including cardiac failure, cardiac failure congestive, cardiopulmonary failure, left ventricular dysfunction, ejection fraction decreased, and right ventricular failure) were reported in 12/672 patients (1.8%) receiving axitinib. Grade 3/4 cardiac failure events were reported in 7/672 patients (1.0%) and fatal cardiac failure events were reported in 2/672 patients (0.3%) receiving axitinib.

Monitoring for cardiac events will include a physical examination and measuring of vital signs at each study visit, in addition to a baseline ECG. Any additional cardiac assessments will be performed when clinically indicated.

### **7.3.5 Concomitant therapy**

#### **CYP3A4/5 inhibitors/inducers**

In vitro data indicate that axitinib is metabolized primarily by CYP3A4/5. Ketoconazole, a strong inhibitor of CYP3A4/5, administered at a dose of 400 mg once daily for 7 days, increased the mean area under the curve (AUC) 2-fold and Cmax 1.5-fold of a single 5-mg oral dose of axitinib in healthy volunteers [Information from Investigator's Brochure, September 2012]. Co-administration of axitinib with strong CYP3A4/5 inhibitors (e.g., ketoconazole, itraconazole, clarithromycin, atazanavir, indinavir, nefazodone, nelfinavir, ritonavir, saquinavir, and telithromycin) may increase axitinib plasma concentrations. Grapefruit may also increase axitinib plasma concentrations. Rifampin, a strong inducer of CYP3A4/5, administered at a dose of 600 mg once daily for 9 days, reduced the mean AUC by 79% and Cmax by 71% of a single 5-mg dose of axitinib in healthy volunteers. Co-administration of axitinib with strong CYP3A4/5 inducers (e.g., rifampin, dexamethasone, phenytoin, carbamazepine, rifabutin, rifapentin, phenobarbital, and Hypericum perforatum [also known as St. John's wort]) may decrease axitinib plasma concentrations. Concomitant medication with strong CYP3A4/5 inhibition potential is therefore not allowed on study.

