As of 1 June 2012, 43 studies evaluating the safety, efficacy, and PK of axitinib have been completed or are ongoing. These studies include 15 Phase 1 studies in healthy subjects and 28 studies in subjects with cancer including 1 continued access and 1 compassionate-use study.

A study in healthy volunteers (A4061007) indicated that the mean absolute oral bioavailability of the drug was 58%. Interaction studies in healthy volunteers with the CYP3A4/5 inhibitor ketoconazole (A4061004) and CYP3A4/5 inducer rifampin (A4061026) produced a 2-fold increase and 79% reduction in axitinib plasma exposures, respectively. Axitinib has two major (non-pharmacologically active) circulating plasma metabolites, a glucuronide product and a sulfoxide product (A4061003). In subjects with moderate hepatic impairment (Child Pugh B), there was a ~2-fold increase in axitinib area under curve from zero to infinity (AUC (0-∞)) and a 1.3-fold increase in axitinib maximum plasma concentration (Cmax) compared to subjects with normal hepatic function (A4061036). No difference in axitinib plasma pharmacokinetics was observed between Caucasian and first-generation Japanese volunteers (n=20 each) (A4061026). Phase 1 studies in combination with chemotherapeutic/anticancer agents in cancer patients have indicated plasma pharmacokinetics of docetaxel, paclitaxel, carboplatin, capecitabine, gemcitabine, cisplatin, pemetrexed, oxaliplatin, 5-fluorouracil (5-FU), bevacizumab, and irinotecan (including its SN-38 activated metabolite) were similar in the absence and presence of axitinib. Likewise, axitinib plasma profiles and pharmacokinetic parameters were similar in the presence and absence of these co-administered chemotherapeutic/anticancer agents (A4061019 and A4061020).

In ongoing clinical studies, the axitinib starting dose is 5 mg BID. Subjects who can tolerate axitinib with no adverse events related to axitinib above Common Terminology Criteria for Adverse Events (CTCAE) Grade 2 for consecutive 2 week periods are permitted to increase their dose step-wise to 7 mg BID and then to a maximum of 10 mg BID, unless their blood pressure (BP) is >150/90 mm Hg. The dose of axitinib can be reduced to as low as 2 mg BID if > Grade 2 treatment-related adverse events occur.

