## 3 Research Strategy

**Primary Objective:** To estimate the objective volumetric response rates to axitinib in pediatric and adult NF2 patients with VS.

**Secondary Objectives:** To assess the toxicity of axitinib given daily in patients with NF2 and to examine the association of objective measures of response on MRI, i.e. volumetric tumor analysis with clinical measures of response, i.e. (audiogram), as well as quality of life assessments (NFTI-QOL). In addition, response in non-VS tumors, such as other schwannomas and meningiomas, may be explored.

**Drug Dosage and Administration (adult patients, age  $\geq$ 18 years):** 5 mg axitinib PO BID, with increase to 7 mg PO BID and 10 mg BID after 2 and 4 weeks, respectively, provided no adverse reactions (i.e., not exceeding grade 2 toxicities) and normotensive and not receiving antihypertension medications. Axitinib will be given continuously in 28-day cycles.

**Drug Dosage and Administration (pediatric patients, age <18 years):** 2.4 mg/m^2 axitinib PO BID, with increase to 3.2 mg/m^2 PO BID after 2 weeks, provided no adverse reactions (i.e., not exceeding grade 2 toxicities) and normotensive and not receiving antihypertensive medications. Axitinib will be given continuously in 28-day cycles using a dosing nomogram shown in Section 7.3.1. The maximal dose of 3.2 mg/m^2 PO BID exceeds the recommended phase 2 dose from the pediatric phase 1 trial, with the rationale that young NF2 patients, who

are generally not pre-treated with myelotoxic chemotherapy are likely to tolerate a higher dose of axitinib compared to the heavily pre-treated, refractory cancer patients enrolled on the pediatric phase 1 study [J Clin Oncol 34, 2016 (suppl; abstr 10558)]. Similar to adult patients on this study, the option to escalate the dose is intended to optimize secondary target inhibition and therefore increase the likelihood of responses.

**Study Assessments:** MRIs including volumetrics and audiograms at baseline and after every 3rd cycle (i.e. 12 weeks). Monthly study visits including H&P, neurological examination and standard laboratory evaluations. Quality of life assessments (NFTI-QOL) at baseline and cycle 6.

**Treatment Duration:** Until radiographic progression or unacceptable toxicity.

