### 7.2.2 Inclusion and exclusion criteria

Patients must have baseline evaluations performed prior to the first dose of study drug and must meet all inclusion and exclusion criteria. Results of all baseline evaluations, which assure that all inclusion and exclusion criteria have been satisfied, must be reviewed by the Principal Investigator or his/her designee prior to enrollment of that patient. In addition, the patient must be thoroughly informed about all aspects of the study, including the study visit schedule and required evaluations and all regulatory requirements for informed consent. The written informed consent must be obtained from the patient (or legal guardian for minors, as applicable) prior to enrollment. The following criteria apply to all patients enrolled onto the study unless otherwise specified.

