### **Exclusion criteria**

- Patients currently receiving medical anticancer therapies or who have received medical anticancer therapies within 4 weeks of the start of study drug (including chemotherapy, antibody based therapy, etc.)
- Radiation therapy to a study target tumor within 1 year prior to enrollment, or any radiation therapy within 4 weeks prior to enrollment.
- Patients who have had a major surgery or significant traumatic injury within 4 weeks of start of study drug, patients who have not recovered from the side effects of any major surgery (defined as requiring general anesthesia) or patients that may require major surgery during the course of the study
- Prior treatment with bevacizumab or other agents targeting VEGF or VEGFR

- Prior treatment with any investigational drug within the preceding 4 weeks
- Unstable or rapidly progressive disease, including patients who require glucocorticoids for symptomatic control of brain or spinal tumors
- Treatment with strong CYP3A4 enzyme inhibitors or inducers, including but not limited to ketoconazole, itraconazole, ritonavir, phenytoin, carbamazepine, rifampin, rifabutin, phenobarbital and St. John's wort. Please refer to the list in Appendix I.
- Requirement of therapeutic anticoagulant therapy with oral vitamin K antagonists; low-dose anticoagulants for maintenance of patency of central venous access device or prevention of deep venous thrombosis is allowed; therapeutic use of low molecular weight heparin (or similar parenteral drug) for venous-thromboembolic disease is allowed.
- Other malignancies within the past 3 years except for adequately treated carcinoma of the cervix or basal or squamous cell carcinomas of the skin.
- Patients who have any severe and/or uncontrolled medical conditions or other conditions that could affect their participation in the study such as:
  - Symptomatic congestive heart failure of New York heart Association Class III or IV
  - unstable angina pectoris, symptomatic congestive heart failure, myocardial infarction within 6 months of start of study drug, serious uncontrolled cardiac arrhythmia or any other clinically significant cardiac disease
  - severely impaired lung function as defined as spirometry and DLCO that is 50% of the normal predicted value and/or O2 saturation that is 90% or less at rest on room air
  - active (acute or chronic) or uncontrolled severe infections

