  - liver disease such as cirrhosis or severe hepatic impairment (Child-Pugh class C).
- Impairment of gastrointestinal function or gastrointestinal disease that may significantly alter the absorption of axitinib (e.g., ulcerative disease, uncontrolled nausea, vomiting, diarrhea, malabsorption syndrome or small bowel resection)
- Patients with an active bleeding diathesis
- Female patients who are pregnant or breast feeding, or adults of reproductive potential who are not using effective birth control methods. Adequate contraception must be used throughout the trial and for 8 weeks after the last dose of study drug, by both sexes. (Females of childbearing potential must have a negative serum pregnancy test within 7 days prior to administration of axitinib)
- Male patient whose sexual partner(s) are women of child bearing potential, who are not willing to use adequate contraception, during the study and for 8 weeks after the end of treatment
- History of noncompliance to medical regimens
- Patients unwilling to or unable to comply with the protocol

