## 13 Statistical Methods

To evaluate efficacy, radiographic response is treated as a binary variable whereby patients who achieve either a CR or a PR in any of the target tumors at any point within 12 months from beginning of therapy are considered responders and all others nonresponders.. A 2-stage Simon design will be used. Axitinib will be considered not of sufficient interest for further evaluation if the true response rate is 5% ( $p_0$ ) or less and considered active if the true response rate is 25% or greater ( $p_1$ ). With beta (probability of rejecting axitinib with true response rate 5%) set at 0.2 and alpha (probability of failing to reject a treatment with response probability of 25%) set at 0.05, the required sample size is 9 patients for stage 1 and an additional 8 patients for stage 2. If there are no responses after the first stage is completed, axitinib will be deemed ineffective and the trial terminated. Recruitment will be halted after the 9th evaluable patient is enrolled (stage 1) until at least one response is observed during the first 12 cycles. Axitinib will be considered effective and of interest for further study if after successful completion of both stages, the cumulative number of responses is  $\geq 3$ . Using this 2-stage design, the probability of early termination is 0.63 if the true response rate to axitinib is 5%.

Stage	Cumulative number of patients with radiographic responses	Decision
Stage 1: enter 9 patients	0	Terminate the trial: agent ineffective
	1 or more	Inconclusive result: continue trial (proceed to Stage 2)
Stage 2: enter 8 additional patients	2 or less	Terminate the trial: agent ineffective
	3 or more	Terminate the trial: agent effective

Disease and patient characteristics at baseline will be summarized using descriptive statistics. For qualitative variables, frequency distributions and proportions will be provided; for quantitative variables, summary statistics (e.g., mean, median, quartiles, standard deviations, etc.) and graphical displays (e.g., boxplots). Overall response rates will be estimated upon completion of the study along with exact 95% confidence intervals.

Secondary endpoints: Audiologic responses will be summarized over time using descriptive statistics and graphical displays. Similarly, quality of life will be summarized over time in these patients.

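### The on-study rule in Section 7.3.5 bans strong CYP3A4/5 inhibitors only, although the same paragraph warns about inducers and entry excludes both classes

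*Combined protocol and SAP*

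**What the plan says.** Four places in the combined protocol and SAP bear on this.

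- **Section 7.3.5, CYP3A4/5 inhibitors/inducers.** The paragraph gives interaction data for ketoconazole (inhibitor) and rifampin (inducer). It names examples of each class and says that inhibitors may raise, and inducers may lower, axitinib concentrations. For rifampin it reports that the drug "reduced the mean AUC by 79" percent. It closes with the operative rule: "Concomitant medication with strong CYP3A4/5 inhibition potential is therefore not allowed on study".
- **Section 7.2.2, Exclusion criteria.** The entry criterion covers both classes: "Treatment with strong CYP3A4 enzyme inhibitors or inducers, including but not limited to ketoconazole", followed by further examples, including six inducers, and a pointer to Appendix I.
- **Section 7.2.2, opening paragraph.** It places the criteria before treatment: "Patients must have baseline evaluations performed prior to the first dose of study drug and must meet all inclusion and exclusion criteria".
- **Appendix I.** It lists both classes but states no rule about use during treatment.

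Two other provisions allow corticosteroids on study. The Steroids paragraph of Section 7.3.5 permits courses of up to 7 days, with dexamethasone as its example, for sudden transient hearing loss. The dose-modification table in Section 7.3.3 suggests a short course for pneumonitis, without giving a length. Section 7.3.5 itself names dexamethasone as a strong inducer.

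**The concern.** The heading, the data and the warnings in the paragraph cover two drug classes, but its rule covers one. No other section expressly bars starting a strong inducer once treatment has begun. An investigator who looks up what is disallowed on study finds inhibitors only.

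Exposure is at stake. The protocol treats dose as relevant to response: in Section 3, "the option to escalate the dose is intended to optimize secondary target inhibition and therefore increase the likelihood of responses". The primary endpoint is binary. Patients with a complete or partial response within 12 months "are considered responders and all others nonresponders" (Section 13). A patient who started a strong inducer and, because of low exposure, never reached a 20% volume reduction would count against the drug.

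**Working it through.** The plan gives no design figure for this point, so the check is mainly a comparison of texts, with one calculation on the interaction data.

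**1. Coverage of each class**

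| Place | Strong inhibitors | Strong inducers | Applies when |
|---|---|---|---|
| Section 1.1, interaction data | yes | yes | background |
| Section 7.2.2, exclusion criterion | excluded | excluded | entry |
| Section 7.3.5, warnings | yes | yes | on study |
| Section 7.3.5, operative rule | banned | not mentioned | on study |
| Appendix I | listed | listed | no rule stated |

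The gap is one cell: inducers under the operative rule.

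**2. Does the entry criterion expressly carry forward?** It does not say so. For contraception, by contrast, the same list states a duration: "Adequate contraception must be used throughout the trial and for 8 weeks after the last dose of study drug". The CYP3A4 criterion has no such words. Continuation can therefore be inferred but is not stated.

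**3. Size of the two interactions.** Section 1.1 summarises ketoconazole and rifampin in turn as having "produced a 2-fold increase and 79% reduction in axitinib plasma exposures". Section 7.3.5 adds Cmax: a 1.5-fold rise with ketoconazole and a 71% fall with rifampin. A fractional reduction r is a fall of 1/(1 − r)-fold.

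- Inducer, AUC: 1/(1 − 0.79) = 1/0.21 = 4.76-fold fall (21% remains).
- Inducer, Cmax: 1/(1 − 0.71) = 1/0.29 = 3.45-fold fall.
- Inhibitor, AUC: 2-fold rise.
- Inhibitor, Cmax: 1.5-fold rise.

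On both measures the class left out of the rule has the larger measured effect. These data come from a single 5 mg dose in healthy volunteers, and rifampin is the only inducer with figures.

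**4. Illustration on the dose scale.** Assume that exposure is proportional to dose and that the effect is as large as rifampin's; the documents establish neither for this setting. Then 5 mg twice daily would act like 5 × 0.21 = 1.05 mg, and 10 mg like 10 × 0.21 = 2.1 mg. The lowest adult dose level in Section 7.3.1 is 2 mg. A weaker inducer would give a smaller shift, down to none.

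**5. Agents the rule should reach.** Appendix I lists 19 inducers, 10 of them marked unknown. Section 7.3.5 names 8 inducers, of which dexamethasone and rifapentin do not appear in Appendix I. A corrected rule therefore needs to point to both places. Because dexamethasone is among the named agents, it must also keep the two existing steroid allowances.

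**The case against.** The strongest reply is that the intent is plain and the ban already exists in substance. The paragraph's heading covers both classes, and the word *therefore* follows directly on the inducer warning. The CYP3A4 exclusion is undated, while neighbouring criteria carry windows such as 4 weeks or 1 year. The next paragraph of Section 7.3.5, on anticoagulants, states its vitamin K antagonist rule purely as ineligibility for enrollment, so the drafters do use an entry criterion as a concomitant-therapy rule. The contraception contrast is also weak evidence, because that sentence had to set a period after the last dose in any case.

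Much of this stands. The omission is probably a drafting slip, and a careful investigator would probably avoid inducers. It does not remove the point: the paragraph does write an on-study rule, and that rule names one class. Nothing elsewhere expressly supplies the other.

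A reader might also infer more than the documents support.

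- **A material loss of power.** Under the stated rule (9 then 8 patients, stop at 0 of 9, active at 3 or more of 17), power at a true 25% response rate is 0.812. If three of the 17 could never respond, placed at random across the stages, it would be 0.691. That calculation does not fit the case. A patient eligible at entry is free of strong inducers then, so has some unaffected exposure first, and a response at any point within 12 months counts. Tolerance-based titration could also offset part of the loss. The number of such patients is invented. The figure deserves no weight.
- **A demonstrated link between low exposure and lost response.** The Section 3 sentence concerns secondary targets, and Section 1.2 says axitinib is much less potent against these than against VEGFR. It does not show that VEGFR-driven responses would be lost.

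**Conclusion.** The point holds as a minor one: an on-study rule that is wrong as written. It rests on the wording alone, namely that both classes are warned about and excluded at entry but only inhibitors are expressly banned during treatment.

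The effect on the trial result cannot be quantified. The documents give no frequency of inducer use, and the effect is nil if no patient starts one. If there is an effect, it runs toward under-exposure and non-response, assuming that lower exposure does not raise the chance of response. It would not favor a false claim of activity. The sample size, decision rule, error rates as designed and estimator are unaffected.

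The visit schedule has no general concomitant-medication row. That is a separate question of data capture, and this conclusion does not depend on it.

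**What to change.** Amend the closing sentence of the CYP3A4/5 paragraph in Section 7.3.5 in three ways:

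1. After *inhibition*, insert *or induction*.
2. After *potential*, insert *(see Appendix I and the agents named above)*.
3. At the end, add *except the short steroid courses permitted under Steroids and in Section 7.3.3*.

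This uses the same Appendix I list as the exclusion criterion, including the entries marked unknown, so entry and on-study rules refer to one list. It also reaches dexamethasone and rifapentin through the agents named in the paragraph. It sets no new limit on the steroid courses already allowed; in particular, it adds no maximum length for pneumonitis, where the plan gives none.

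The cost is one written amendment under Section 8. No visits, tests or patients are added. The clinical downside is that a patient who comes to need a strong inducer must use an alternative or stop axitinib.
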